4.13.4 Local Tolerability

Subject assessment of tolerability will be displayed with investigator assessment of tolerability.

Subgroup analyses of local tolerability will include the subgroups listed for TEAEs in [Section 4.13.3](#) of this SAP. The local tolerability assessments during the surgery and subcutaneous substudies will not be included. Analyses of local tolerability will exclude tolerability assessments during the surgery and subcutaneous substudies.

4.13.5 Laboratory Safety Parameters

Laboratory results along with the change from baseline will be summarized by parameter and study visit. The change from baseline to the lowest value after first dose of study product, highest value after first dose of study product, and final value will also be summarized. For laboratory parameters with positive or negative results, the number and proportion with positive treatment-emergent results will be summarized at each visit.

Laboratory values will be converted to the standard units of measurement for summary displays.

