If a bleeding episode occurs, whether spontaneous or as the result of trauma or injury, **ONLY** the injury should be recorded as an AE or SAE. The bleeding episode, whether spontaneous or resulting from the injury, should not be recorded as an AE, but as a bleeding episode on the appropriate eCRF page.

For laboratory safety parameters, any instances of absolute values being outside the reference range or changes at any visit after study start that are considered by the investigator as clinically significant must be recorded in the eCRF as AEs. In addition, at the investigator's discretion, any changes or trends over time in laboratory parameters can be recorded in the eCRF as AEs if such changes or trends are considered to be clinically relevant, even if the absolute values are within the reference range.

Laboratory findings do not need to be reported as AEs in the following cases:

- Laboratory parameters already beyond the reference range at Day 1 of the lead-in study (subjects in Arms 1 or 2) or at screening (subjects in Arm 3 or Arm 4), unless a further increase/decrease can be considered an exacerbation of a pre-existing condition.
- Abnormal laboratory parameters caused by mechanical or physical influences on the blood sample (eg, in vitro hemolysis) and flagged as such by the laboratory in the laboratory report.
- Abnormal parameters that are obviously biologically implausible (eg, values that are incompatible with life or outside the measuring range).
- An abnormal laboratory value that cannot be confirmed after repeat analysis, preferably in the same laboratory (ie, the previous result could be marked as not valid and should not necessarily be reported as an AE).

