11.3.3.4 Laboratory Safety Parameters

Laboratory results along with the change from baseline will be summarized by parameter and study visit. The change from baseline to the smallest value after first dose of study product, largest value after first dose of study product, and final value will also be summarized. For laboratory parameters with positive or negative results, the number and proportion with positive study-emergent results will be summarized at each visit.

The number and proportion of subjects with study-emergent abnormal laboratory values will be tabulated. Study-emergent abnormal laboratory values are those in which the baseline value is normal and post-baseline value is abnormal. Laboratory values will be converted to the project-defined unit of measurement.

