This document presents the statistical analysis plan (SAP) for CSL Behring GmbH, Protocol No. CSL654_3003: A Phase 3b Open-label, Multicenter, Safety and Efficacy Extension Study of a Recombinant Coagulation Factor IX Albumin Fusion Protein (rIX-FP) in Subjects with Hemophilia B.

This analysis plan is based on the protocol amendment 6 dated 03 February 2020, final electronic case report form (eCRF) dated 17 May 2017, and the SAP version 3 dated 20 April 2018. This SAP contains all analyses for the previously treated patients (PTPs), and the updated contents for the previously untreated patients (PUPs).

In the event that the statistical methods specified in this SAP differ from those specified in the protocol, the statistical methods specified in the SAP will supersede the statistical methods described in the protocol.

2 Study Objectives

- Main Study
 - Primary Objective
 - The primary objective of this study is to evaluate the safety of rIX-FP as measured by new cases of inhibitors against FIX in subjects, including PUPs, with severe hemophilia B. The PK parameters in PUPs will also be collected.
 - Primary Endpoint(s)
 - The total number of subjects who develop inhibitors against FIX during the approximately 5-year participation in this study.
 - PK parameter of incremental recovery (IU/dL per IU/kg) of 50 IU/kg rIX-FP (Arm 4 only)
 - Secondary Objective(s)

[figure not shown]
The secondary objectives of the study are:

 - To evaluate the efficacy of rIX-FP routine prophylaxis when administered at various treatment intervals.
 - To compare the efficacy of rIX-FP routine prophylaxis between 2 different treatment intervals and versus on-demand treatment.
 - To further evaluate the safety of rIX-FP.
 - To evaluate the efficacy of treatment for bleeding episodes in PUPs.
 - Secondary Endpoint(s)
 - Annualized bleeding rate (ABR) for spontaneous treated and total treated bleeds for each assigned treatment interval (7 days, 10 days, 14 days, and 21 days).
 - Comparison of the annualized spontaneous bleeding rate (AsBR) and ABR between:

- 14-day routine prophylactic treatment in this study compared with on-demand only treatment from Study CSL654_3001 Arm 2.
- 7-day prophylaxis regimen with the 14-day prophylaxis regimen.
- 7-day prophylaxis regimen with the extended prophylaxis regimen (10-day or 14-day).
- Total number of exposure days of rIX-FP
- Consumption of rIX-FP during routine prophylaxis expressed as IU/kg per month per subject.

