The analysis of safety and efficacy for subjects ≥ 18 years in 21-day regimen, and subjects < 12 years in 14-day regimen were added to explore the prevention of bleeds in those longer prophylaxis regimens.

The endpoint of total number of exposure days of rIX-FP has been added as a secondary endpoint.

The estimate of ABRs and AsBRs (including 95% CI) are using negative binomial model as main analysis, and Poisson model as sensitivity analysis due to half of the subjects are expected to have zero bleedings (over-dispersed).

In protocol section 11.3.2.2, states that the AsBR and ABR will be derived for each regimen assigned to the subject, and will not include the time either during or the first 3 months after the surgery substudy, etc. To be consistent with pivotal studies (3001 and 3002), the AsBR and ABR will include the first 3 months after the surgery substudy.

Deviations from the protocol-stated analyses for PUPs in Protocol CSL654_3003 (Amendment 6) are summarized below:

Annualized bleeding rate for treated spontaneous bleeds and treated total bleeds will be derived and listed per subject and regimen. No comparison of AsBR or ABR between regimens will be carried out.

Deviations from SAP- stated Analyses

Any deviations from the original statistical plan will be described and justified in the final clinical study report (CSR), whether written post interim or final analysis.

9 Tables Figures, and Listings

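### SAP 4.13.5 leaves out the protocol's count of subjects with new laboratory abnormalities, and SAP Section 8 does not declare the change

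*SAP*

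**What the plan says.** Protocol 11.3.3.4 plans the following: "The number and proportion of subjects with study-emergent abnormal laboratory values will be tabulated". It also defines the category: "Study-emergent abnormal laboratory values are those in which the baseline value is normal and post-baseline value is abnormal". It names no reference range.

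SAP 4.13.5 covers the same ground. It starts with "Laboratory results along with the change from baseline will be summarized by parameter and study visit" and goes on to "The change from baseline to the lowest value after first dose of study product, highest value after first dose of study product, and final value". For tests reported as positive or negative, "the number and proportion with positive treatment-emergent results will be summarized at each visit". It ends with conversion of units. Nothing in it counts subjects who move from normal to abnormal on a quantitative test.

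The SAP introduction settles conflicts between the two documents: "the statistical methods specified in the SAP will supersede the statistical methods described in the protocol". SAP Section 8 lists the departures from the protocol. For PUPs the list concerns bleeding rates only: "Annualized bleeding rate for treated spontaneous bleeds and treated total bleeds will be derived and listed per subject and regimen", with no comparison between regimens. The list for previously treated patients (PTPs) does not mention a laboratory table either.

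**The concern.** A protocol-specified safety output is absent from the SAP with no reason given. Change from baseline and new abnormality answer different questions. The first describes how far values moved; the second says how many subjects left the normal range. An Arm 4 reader will want the second, because the cohort is small, young and uncontrolled, and no comparator shows what change to expect.

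Without the table, a child whose liver or renal values become abnormal is counted only if the investigator judges the finding clinically significant and records an adverse event. That is a judgement made site by site. The protocol's table would not depend on it.

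**Working it through.** No power, error rate or event count is involved, so the check is a comparison of texts.

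| Element of Protocol 11.3.3.4 | In SAP 4.13.5? |
|---|---|
| Results and change from baseline, by parameter and visit | Yes |
| Change to smallest, largest and final value | Yes |
| Emergent positives for positive/negative tests | Yes |
| Number and proportion with a normal baseline and an abnormal later value | **No** |
| Conversion of units | Yes |

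Four of five elements are carried over, nearly word for word.

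**Is the table elsewhere in the SAP?** No. The SAP text contains no laboratory shift table and no classification against a reference range. The nearest analogue is SAP 4.13.7, which tabulates potentially clinically significant vital signs but says that this is for PTPs. There the narrowing is at least written out. In the laboratory section the table is simply absent.

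**Is the removal declared?** No. Section 8 has separate lists for PTPs and PUPs, and neither mentions it. The precedence clause decides which document governs; it does not explain the change.

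**What still reports on laboratory values in Arm 4?**
- Observed values and changes by visit, and changes to the lowest, highest and final value. SAP 4.1 and 9.1 require the minimum and maximum as well as the mean.
- Emergent positives on qualitative tests.
- Supporting listings where applicable (SAP 4.1).
- Adverse events. Under Protocol 9.1.1, values outside the range, or changes, that are "considered by the investigator as clinically significant must be recorded in the eCRF as AEs" go on to the treatment-emergent tables of SAP 4.13.3.

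**What do these not supply?** A count. The maximum change shows the largest movement, but not whether that value left the normal range or how many other subjects did. The largest rise may stay within range while a smaller one crosses the limit.

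**Scale.** If *m* PUPs have both a baseline and a post-baseline value for a parameter, one child with a new abnormality is 1/*m* of the table. With *m* = 13, the planned minimum enrolment, that is 1/13 = 7.7%. The true *m* is unknown. Protocol 8.9.1.2 takes screening samples where feasible or accepts results up to 6 months old, so some children may lack a usable baseline, and enrolment may exceed 13. The figure is an illustration only.

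**The case against.** The strongest reply is that little is lost. Observed values stay, the required minimum and maximum can expose an outlying child, listings of about 13 children can be read line by line, and clinically significant findings must be reported as adverse events. Laboratory shifts are neither a primary nor a named secondary endpoint, and safety analysis is descriptive. All of this stands, and it makes the point a modest one. It does not replace a systematic count or explain why a planned table was removed.

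Four stronger readings are tempting and should be resisted.

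- A reader might infer that only raw changes from baseline are left. SAP 4.13.5 itself keeps observed results and qualitative positives.
- A reader might infer that growth confounds the Arm 4 laboratory changes. It is reasonable to assume that growth and differences between local laboratories make mean changes harder to interpret over about 3 years, with no covariate adjustment (SAP 4.1.6). Neither document gives paediatric norms or age trends, so the size of the effect is unknown. The protocol's table would help with this only if suitable reference ranges were used, and the protocol specifies none.
- A reader might set 1/13 of the table against 1/13 of one child's change in the mean as the measure of the loss. That ignores the minimum and maximum and assumes that all 13 PUPs are evaluable.
- A reader might infer that the table will certainly not be produced. SAP 9.2 puts the list of tables in a separate document, so the table may be in the shells.

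**Conclusion.** The omission is real and undeclared. On the written plan, Arm 4 has no systematic count of new quantitative laboratory abnormalities. The size is one missing element out of five, in a descriptive safety section whose other outputs are intact. No primary or secondary endpoint is affected.

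The practical consequence is confined to PUPs. The omission covers PTPs too, but SAP 3.1 says that Arms 1 to 3 were already reported in a study report dated 14 March 2019, and SAP 3.4 says that this version focuses on Arm 4. The conclusion rests on the SAP text as written. If the shells already contain the table, only the text needs correcting. The point is worth making because the remedy is cheap and the cohort is small, young and uncontrolled.

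**What to change.** In SAP 4.13.5, restore the protocol's analysis for Arm 4:
- Give, by parameter, the number and proportion of subjects with a normal baseline and at least one abnormal post-baseline value, among subjects with both a baseline and a post-baseline value.
- State the reference range. The range of the local laboratory that ran the test, age-appropriate where available, is the natural choice. This goes beyond the protocol, which says only normal and abnormal.
- Flag abnormal values in the supporting listing.

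If the removal was intended, declare it in Section 8 and give the reason.

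The cost is one additional standard table from results already collected. The condition is that local reference ranges are in the database, which the documents do not confirm. If some are missing, the table should say how many values could not be classified.

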4.13.6 Antibodies to rIX-FP and CHO Cell-derived Proteins

The number and percentage of subjects with rIX-FP and CHO cell-derived protein antibody titers above the cut-off level for the respective confirmation assays will be tabulated.

4.13.7 Vital Signs

Vital signs (systolic blood pressure [SBP], diastolic blood pressure [DBP], pulse rate, and temperature) results along with the change from baseline will be summarized by parameter and study visit. The number and proportion of subjects with treatment-emergent potentially clinically significant (PCS) vital sign values by study visit will be tabulated for PTPs. Criteria for PCS values will be derived in the analysis dataset and summarized by study visit according to the criteria in Table 8.

Table 8. Criteria for Potentially Clinically Significant Vital Sign Results

Vital Sign	Criteria	Definition of PCS
Systolic Blood Pressure	Low	values ≤ 90 mmHg and decreased ≥ 20 mmHg from initial value
	High	values ≥ 180 mmHg and increased ≥ 20 mmHg from initial value

Diastolic Blood Pressure	Low	values ≤ 50 mmHg and decreased ≥ 15 mmHg from initial value
	High	values ≥ 105 mmHg and increased ≥ 15 mmHg from initial value
Heart Rate	Low	values ≤ 50 bpm and decreased ≥ 15 bpm from initial value
	High	values ≥ 120 bpm and increased ≥ 15 bpm from initial value

4.13.8 Virus Safety

Results from virus safety samples will be listed.

4.13.9 Additional Safety Information from the Surgery Substudy

Safety assessments and events, including AEs that occur during the preoperative, intraoperative, or postoperative periods of the surgery substudy will be summarized in separate tables ([Section 6.7.7](#)).

4.13.10 Additional Safety Information from the Subcutaneous Substudy

Safety assessments and events, including AEs that occur during the SC substudy will be summarized in separate tables ([Section 7](#)).

4.14 Pharmacokinetics and Pharmacodynamics Data

4.14.1 Pharmacokinetics

A non-compartmental analysis (NCA) will be performed on plasma FIX activity using WinNonlin® 6.2.1 or higher. The PK parameters will be derived with and without correction for baseline FIX levels. Baseline levels are defined as the pre-dose levels before a specific product administration. Descriptive statistics will be presented for both baseline-corrected and uncorrected NCA PK parameters. In the event that considerable residual levels of previous product (e.g. due to prior rIX-FP dosing) are evident at pre-dose, calculations of baseline-corrected PK parameters (by subtraction of the pre-dose FIX activity level from subsequent post-dose levels) may be limited to incremental recovery (IR), C_{max} , and t_{max} .

Incremental recovery will be calculated using the PK samples obtained following injection of 100 IU/kg rIX-FP for PTPs or 50 IU/kg rIX-FP for PUPs. Incremental recovery (IU/mL/IU/kg) is defined as FIX activity (IU/mL) obtained 30 minutes following injection, per dose of (IU/kg) injection. IR and FIX activity levels will be summarized.

The PK endpoints are:

- Observed trough (pre-dose) and steady-state PK FIX activity.
- PK parameters: IR, C_{max} , t_{max} , AUC_{last} , $AUC_{0-\infty}$, AUC_{ext} , λ_z , λ_z (Lower), λ_z (Upper), $t_{1/2}$, CL, CL/BW, V_z , V_z/BW , V_{ss} , V_{ss}/BW , MRT and $AUMC_{0-\infty}$.

Population PK modeling and simulation will also be performed. A separate Modeling Analysis Plan (MAP) will further define the population PK analysis, parameters and simulation methods, and these model results will be summarized in a separate supplemental report.

FIX activity levels from central and local laboratories will be summarized with descriptive statistics and listed by subject and assessment time point. Trough levels will be summarized by regimen.

Trough and steady-state flags will be derived for the observed PK FIX activity.

The following FIX results will be excluded from the derivation of the trough FIX:

- Any FIX activity measured at a local lab
- Any FIX activity measured during PK, repeated PK, surgical and subcutaneous periods
- Any FIX activity measured during an unscheduled visit
- If there are any additional doses administered (such as treating a bleeding event or additional dose) between 2 prophylaxis dose time intervals, the FIX activity measured before the second prophylaxis dose will be excluded.

Steady-state FIX is the subset of trough FIX. Two additional conditions will be applied to trough FIX values to derive the steady-state FIX:

- FIX trough samples that are not after the following will be excluded
 - 1 consecutive dose on 21-day regimen or
 - 2 consecutive doses on the 14-day or 10-day regimens or
 - 3 consecutive doses on the 7-day regimen
- If additional FIX product is administered (e.g. rescue), the subsequent trough FIX value occurring within 21 days for the 21-day regimen, 28 days for 14-day or 10-day regimens, or 21 days for the 7-day regimen will be excluded as the washout period for rIX-FP is about 5 half-lives.

Descriptive statistics for the observed trough and steady state PK FIX results will be provided for all prophylaxis regimens overall and by age ([Section 4.1.1](#))

4.14.2 Additional Pharmacokinetic Information from the Subcutaneous Substudy

The PK assessments of rIX-FP which occur during the PK period of the subcutaneous substudy will be summarized in separate tables ([Section 7.6.2](#)).

4.14.3 Pharmacodynamics

Not applicable.

4.15 Other Analyses

Not applicable.

5 Subset Analyses of Japanese Subjects

Subset analyses will be performed for Japanese subjects. All analyses of Japanese subjects will be based on the subjects who were enrolled in Japan.

Summaries from the main study as applicable will be repeated for the Japanese subset of subjects for the following:

- subject disposition
- protocol deviations
- demographics and baseline characteristics
- prior on concomitant Medications
- exposure and time on study
- compliance
- ABRs for each bleeding event type
- consumption during routine prophylaxis
- investigator's assessment of hemostatic efficacy
- number of bleeding events
- FIX activity concentrations
- uncorrected and baseline-corrected FIX activity PK parameters following administration of rIX-FP by dose
- FIX activity trough and steady state
- TEAEs (summary and by SOC and PT) as follows:
 - TEAEs
 - all SAEs.
 - related TEAEs
 - related treatment-emergent SAEs
 - TEAEs by maximum severity. If a subject experiences multiple events that map to a single PT, only the most severe event will be counted.
 - TEAEs by relationship. If a subject experiences multiple events that map to a single PT, only the related event will be counted.
 - TEAEs occurring ≤ 72 h after infusion
 - TEAEs leading to withdrawal of study medication and by regimen
 - TEAEs due to death
 - TEAEs occurring in $\geq 2\%$ of subjects
 - TEAE by every 6-month interval
- local tolerability

- inhibitors and antibodies to FIX
- laboratory results – hematology and biochemistry
- vital signs
- non-pharmacologic interventions

Analyses of exposure, TEAEs, and local tolerability will be presented for the Japanese subjects ≥ 18 years of age who switched from the 14-day regimen to the 21-day regimen in Study CSL654_3003 and for Japanese subjects ≥ 12 years of age who did not switch.

The following analyses of ABR and AsBR will be presented for Japanese subjects:

- subjects ≥ 18 years in both the 21-day and 7-day regimens
- subjects ≥ 18 years in both the 21-day and 14-day regimens

No hypothesis tests will be presented for the Japanese subset due to the limited number of Japanese subjects in each regimen. Point estimates and 95% CIs will be presented if estimable.

Separate listings for Japanese subjects in the main study will not be produced as all listings for the study will include country and race. Analyses of Japanese subjects in the surgery substudy will be presented in subject listings. No Japanese subjects participated in the SC substudy.

Figures for PK/FIX activity for Japanese subjects will be provided if applicable (i.e. number of Japanese subjects with FIX activity based on the 50 and 100 IU/kg doses).

6 Surgery Substudy

6.1 Introduction

This substudy of Study CSL654_3003 will examine the efficacy of rIX-FP in subjects with severe hemophilia B who are undergoing non-emergency major or minor surgery. The efficacy endpoint, investigator's (or surgeon's) overall clinical assessment of hemostatic efficacy, will be measured during surgical periods. The safety endpoints, including antibodies against rIX-FP, inhibitors to FIX, and other AEs throughout the duration of the study will be provided.

The substudy will be conducted in compliance with this study protocol, ICH Good Clinical Practice (GCP), and the applicable regulatory requirement(s).

